SADE	Serious Adverse Device Event
Study Subject	An individual that has signed a HIPAA form and an IRB approved study consent form
Subject	Individual being considered for enrollment in to the study
UP	Unanticipated Problem

STUDY SYNOPSIS

Study Protocol Number: NDE68-19-01

Study Protocol Title: An Open-Label, Multi-Center Clinical Study Evaluating the Effect of the NDE L68 StableFit® Punctal Plug on the Tear Lake

Sponsor: Mati Therapeutics Inc.

Investigational Product, Open-Label: Mati's Non-Significant Risk, Non-Drug Eluting (NDE) L68 StableFit® punctal plug design. The NDE L68 StableFit® punctal plug is pre-loaded onto a disposable inserter and individually packaged and sterilized to prevent contamination. The L68 StableFit® plug consists of medical grade silicone and 2% green colorant. The L68 StableFit® plug is stored at room temperature.

Number of sites: Up to 4 sites within the U.S.A.

Study Population: Up to 40 male or female subjects in good general health with a mild to moderate dry eye condition. A subject will be allowed to use ocular drops during the study however, the subject must discontinue the use of all drops at least one hour prior to a study examination.

Study Objective: To evaluate the effect of the NDE L68 StableFit® punctal plug on the tear lake. In addition, evaluate the insertion/removal characteristics and the investigator's evaluation of the subjects' acceptance of the NDE L68 StableFit® punctal plug.

Study Design: This is a Non-Significant Risk (NSR) medical device, multi-center, open-label clinical study. Each study subject that qualifies at the baseline visit will receive an NDE L68 StableFit® punctal plug in the lower punctum in one of their eyes. All study plugs will remain in the study subject's lower punctum for a period of 28 + 4 days after insertion.

Note: The investigator has the option of inserting the plug in either the left or right eye of the subject. However, if the investigator is unable to insert the plug in the first eye chosen, the investigator can insert the plug in the fellow eye as long as the fellow eye meets all study inclusion/exclusion criteria.

Subject Selection: The following are inclusion and exclusion criteria for a prospective study subject

Study Inclusion Criteria: The following are inclusion criteria for potential study subjects' wishing to participate in this study

- a. A male or female subject, 18 years of age or older, in good general health at the time of the baseline examination, who may or may not have a mild to moderate dry eye condition
- b. A subject must be able to read, comprehend and be willing to give HIPAA authorization and informed consent

- c. A subject must be willing to have a punctal plug inserted in the lower punctum of one of their eyes
- d. A subject must be willing to comply with all study instructions, agree to make all office appointments, and complete the entire course of the study

Subject Exclusion Criteria: The following are exclusion criteria for potential study subjects' wishing to participate in this study:

- a. A subject with a history of complications, adverse events, trauma or disease in the nasolacrimal area, whether or not it was due to punctal plug wear, including but not limited to dacryocystitis, inflammation or canaliculitis in the planned study eye
- b. A subject with a history of intolerance to punctal plugs
- c. A subject with structural lid abnormalities (e.g., ectropion, entropion) in the planned study eye
- d. A subject with any clinically significant lid, conjunctival or corneal findings in the planned study eye at the baseline visit
- e. A subject with a puncta >0.9 mm prior to dilation in the planned study eye
- f. A subject with a severe dry eye condition
- g. A subject experiencing epiphora in the planned study eye
- h. A subject experiencing any clinically significant ocular pain or discomfort in or around either eye at the baseline visit
- i. A subject with a known sensitivity to any inactive ingredient of the punctal plug, silicone, topical anesthetic, or any other products required for the study
- j. A subject currently participating or has participated in a clinical trial involving the use of an investigational medication within 30 days prior to enrollment.

Study Duration: The approximate study duration is eight months. The study is projected to start the 3rd quarter of 2019

Study Variables: The following will be performed and/or recorded during the course of the study

Visit 1: Screening/Baseline (Day 0)

- a. Obtain written Consent and HIPAA
- b. Subject demographic data and medical history for past 7 days
- c. Verify a subject has not used any ocular drops within the last hour prior to their baseline visit

- d. Record subject reports of any ocular signs or symptoms they are currently experiencing, prior to the sizing and dilation of the lower punctum
- e. Slit-Lamp examination of the planned study eye, prior to the sizing and dilation of the lower punctum
- f. Tear lake evaluation of the planned study eye, prior to the sizing and dilation of the lower punctum
- g. Size evaluation of the lower puncta of the planned study eye, prior to dilation of the lower punctum
- h. After dilation of the punctum to at least 1.0 mm, insert the study punctal plug
- i. Inspection of the punctal plug after insertion via slit-lamp
- j. Record any Adverse Device Events
- k. After a study subject has been inserted with the NDE L68 StableFit® punctal plug, the Investigator will evaluate the insertion characteristics of the punctal plug

NOTE: After the last study subject has been inserted with a study punctal plug, based on all subjects enrolled in the study, the investigator will give an overall assessment on the insertion characteristics of the study punctal plug.

Visit 2: Follow-up (Day 7 + 1 post plug insertion)

- a. Verify a subject has not used any ocular drops, in their study eye, within the last hour prior to their scheduled visit
- b. Slit Lamp examination
- c. Inspection of the plug via slit-lamp
- d. Tear lake evaluation
- e. Record any Adverse Device Events

Visit 3: Follow-up (Day 28 + 4 post plug insertion)

- a. Verify a subject has not used any ocular drops, in their study eye, within the last hour prior to their scheduled visit
- b. Investigator evaluation of the subject's acceptability of the punctal plug, prior to removal of the study plug
- c. Slit Lamp examination, prior to removal of the study plug
- d. Inspection of plug via slit-lamp, prior to removal of the study plug

- e. Tear lake evaluation, prior to removal of the study plug
- f. Remove study punctal plug
- g. After the plug has been removed, the Investigator will evaluate the removal characteristics of the inserted punctal plug
- h. Record any Adverse Device Events

NOTE: After the last study subject has had their punctal plug removed, based on all subjects that completed the study, the investigator will give an overall assessment on the removal characteristics of the punctal plug.

Study Outcome Variables:

Primary Study Endpoint: Investigators' evaluation of the tear lake

Secondary Study Endpoint: Investigator's evaluation of epiphora, insertion/ removal characteristics and Investigators' evaluation of the subject's acceptance of the NDE L68 StableFit® punctal plug.

Study Safety Variables: Safety assessments will include any clinically significant slit-lamp biomicroscopy findings, any extrusions of a punctal plug and incidence and severity of any reported ADEs after punctal plug insertion.

Sample Size Determination: Since this is a pilot study, no formal sample size estimation was performed.

Schedule of Assessments, Events

EXAM PARAMETERS	v1	v2	v3
Inform Consent/HIPAA	①		
Demographic Data/Medical Hx	① A		
Subject Reports of any Ocular Signs or Symptoms	① B		
Verify No Ocular Drop use One Hour Prior to Visit	①	②	③
Inv. Evaluation of Subject's Acceptance of Study Plug			③ C
Slit Lamp Examination	① B	②	③ C
Tear Lake Evaluation	① B	②	③ C
Size Evaluation of Lower Puncta, Prior to Dilation	① B		
Dilation of Lower Puncta	①		
Insertion of a Punctal Plug	①		
Inspection of the Placement of the Punctal Plug	① D	②	③ C
Investigator Device Assessment of Insertion	① E		
Removal of Punctal Plug			③
Investigator Device Assessment of Removal			③ F
Adverse Device Event Recording	①	②	③

Keys to Abbreviations:

A = Record medical history for the past 7 days

B = PRIOR to **INSERTION** of punctal plug

C = PRIOR to **REMOVAL** of punctal plug

D = Slit-Lamp Evaluation of Punctal Plug **AFTER INSERTION**

E = After EACH Study Subject and after **ALL** Study Subjects have had their Punctal Plug Inserted

F = After EACH Study Subject and after **ALL** Study Subjects have had their Punctal Plug Removed

Visit Schedule:

v1 = Screening/Baseline

v2 = 7 ± 1 days post plug insertion

v3 = 28 ± 4 days post plug insertion

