4 STUDY DESIGN AND ENDPOINTS

4.1 Description of the Study Design

This is a Non-Significant Risk (NSR) medical device, multi-center, open-label clinical study. Each study subject that qualifies at the baseline visit will receive an NDE L68 StableFit® punctal plug in the lower punctum in one of their eyes. All study plugs will remain in the study subject's lower punctum for a period of 28 + 4 days after insertion.

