5.4 Strategies for Recruitment and Retention

To increase study subject enrollment and retention in the study, sites should dedicate an individual [Clinical Research Coordinator (CRC)] who is well informed regarding the study design, study specific inclusion/exclusion criteria and visit schedule as the main contact who is readily available to answer all potential subject questions and/or concerns about participating in the clinical study.

The CRC should be prepared to discuss with a potential study subject the differences in the amount of time, examination procedures and visit schedule they would experience if they agreed to participate in the study. In addition, should a subject agree to participate in the study, the CRC would be readily available as his/her main contact person while participating in the study.

To encourage recruitment and retention of a study subject, sites should offer a subject reimbursement for transportation cost and a stipend for his/her time and effort for participation, offer less waiting time in the doctor's office by scheduling more flexible and reliable appointment times.

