7.2 Study Procedures/Evaluations

7.2.1 Study Specific Procedures

Procedures that are required during the course of the study include:

- a. Informed consent and HIPAA authorization: The Investigator and or qualified staff will review and answer any questions a potential study subject may have regarding the study, the consent or HIPAA authorization forms. Prior to the initiation of any study specific activities, the subject must sign both documents
- b. Record subject's demographic data and medical history for the previous 7 days
- c. Record any subject reports of any ocular signs or symptoms they may be experiencing
- d. Slit-Lamp Examination: Slit-lamp examination will include assessment of the lid, conjunctiva and cornea as normal or abnormal. If a finding is indicated as abnormal, the investigator will indicate if the finding is clinically significant. If the finding is considered clinical significant, the investigator will describe the finding in the section provided on the Case Report form
- e. Evaluation of the subject tear lake: Using a slit lamp micrometer, the micrometer will be oriented vertically and centered on the lower lid margin at the middle of the lower lid. The tear lake will be measured using the slit lamp micrometer from the lid margin to the superior border of the lower tear lake and measured to 0.1 mm.
- f. Punctum size evaluation prior to dilation: Using the Coroneo punctum dilator, the narrow end of the dilator has calibrated rings that correspond to punctum diameters of 0.5, 0.6 and 0.7 mm. The rings on the wide end of the dilator correspond to punctum diameters of 0.8, 0.9 and 1.0 mm. Prior to measuring the punctum diameter, the eye should be anesthetized (see [Section 6.2](#) of the protocol for details) with a topical anesthetic. The narrow end of the dilator is then introduced vertically into the punctum and advanced until the punctum starts to invert. The diameter is recorded as the nearest ring to the edge of the punctum when inversion begins. If the punctum diameter is larger than 0.7 mm, the narrow end of the dilator is removed, and the wider end inserted and advanced in the same way. Again, the diameter is recorded as the nearest ring when inversion begins.
- g. Insertion of a study punctal plug (see [Section 6.2](#) of the protocol for details)
- h. Removal of a study punctal plug (see [Section 6.6](#) of the protocol for details)

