7.3.3 Visit 2: Follow-Up (Day 7 + 1 post plug insertion)

At this visit the following will be performed and recorded:

- a. Verify a subject has not used any ocular drops, in their study eye, within the last hour prior to their scheduled visit
- b. Slit-lamp examination of the study eye
- c. Inspection of the punctal plug via the slit lamp
- d. Tear lake evaluation of the study eye
- e. Recording of any reported adverse device event(s)

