10.3 Analysis Datasets

Data will be pooled from all study centers for data analysis, unless otherwise specified. Study dataset will be generated (keypunched) from original (white) case report forms that have been reviewed and collected from clinical sites. Dataset will contain rows of individual subject data; each row will be clearly labeled with the study subject ID number and initials. Each column of the dataset will contain a specific parameter for all study subjects.

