10.4.2 Analysis of the Primary Endpoint(s)

The primary study variable will be based on the change from baseline in tear lake values. For analyses, using the intent-to-treat (ITT) data set, all data from all subjects with at least one follow-up evaluation of the tear lake will be evaluated. For the per protocol (PP) analyses dataset, data from subjects or visits with significant protocol deviations will be excluded.

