11.4 Case Report Form Completion

The Investigator is responsible for ensuring that data are properly recorded on each study subject's case report forms and related documents. An Investigator who has signed the protocol signature page should personally sign completed case report forms to ensure that the observations and findings are recorded on the case report forms correctly and completely. Following study examination, investigative sites should complete and remove the yellow NCR copy of the CRF from the study subjects' booklet leaving the white copy of the CRF intact inside the booklet. Yellow copies of completed CRFs will be mailed in on a weekly basis to the following:

D'Ellis Group, Inc.
Attn: [name]
[name]
[name]

The CRF data will be reviewed against the subject's source data by the study monitors to ensure completeness and accuracy. After monitoring has occurred at the clinical sites and the CRFs have been submitted, additional data clarifications and/or additions may be needed. Data clarifications and/or additions are documented and are part of each subject's CRFs.

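### Nothing stops the unmasked examiner from seeing the Day 0 tear lake value before making a follow-up reading, so the primary change score can be influenced by the earlier number; a blind-to-baseline reading rule is a cheap, partial safeguard.

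*Combined protocol and SAP*

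**What the plan says.** **Who reads, and what is analysed.** The Synopsis gives "Primary Study Endpoint: Investigators' evaluation of the tear lake". Section 10.4.2 states: "The primary study variable will be based on the change from baseline in tear lake values". Section 4.1 describes the design: "This is a Non-Significant Risk (NSR) medical device, multi-center, open-label clinical study". Every qualifying subject receives the plug in one eye, and no untreated arm or eye is measured for comparison.

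**How it is read.** Section 7.2.1(e) has the height taken with a slit-lamp micrometer "from the lid margin to the superior border of the lower tear lake and measured to 0.1 mm". No repeat reading, image, second reader or masked reader is described.

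**Where the Day 0 value is kept.** After each examination the yellow copy is removed and mailed, "leaving the white copy of the CRF intact inside the booklet" (Section 11.4). Section 10.3 says the dataset comes from "original (white) case report forms that have been reviewed and collected from clinical sites", without saying when collection takes place. Section 11.1 requires source documents that are distinct from the CRF, unless the sponsor has allowed direct CRF entry, and these are to hold the relevant observations on the subject.

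**What happens at follow-up.** At Visit 2 (Section 7.3.3) the item "Inspection of the punctal plug via the slit lamp" is listed directly before the tear lake evaluation. Visit 3 and Early Exit list them in the same order. None of these lists withholds an earlier tear lake value.

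**The concern.** The primary result is the difference between two visual readings on a scale with 0.1 mm steps, made by someone who knows that a plug is in place. Section 2.1 describes plugs as conserving tears by occlusion, so the expected direction is upward. If the Day 0 number is in view, the examiner knows which step would count as an increase, and a borderline reading may be settled with that knowledge.

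An error of this kind, if it has a consistent direction, does not average out over subjects. It enters the mean change, and with no control arm or control eye nothing subtracts it. Section 10.2.1 sets a formal null hypothesis of no difference and Section 10.4.1 a two-sided 5% level, so a false rejection is possible even though the study is called a pilot. The plug cannot be hidden from the examiner, but the earlier number can.

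**Working it through.** The plan has no sample-size or power figure to reproduce (Section 10.5) and names no test for the primary comparison. The check asks how much shading would matter.

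**Inputs from the documents:** up to 40 subjects, 40 eyes (Section 4.2); two-sided 5% (Section 10.4.1); reading step 0.1 mm (Section 7.2.1(e)).

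**Assumptions:** one-sample t-test on the change at one follow-up visit; n = 40; true change zero; SD of change before shading 0.10, 0.15, 0.20 or 0.30 mm (the documents give none); a random fraction f of follow-up readings moved up one step.

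**Step 1: smallest mean change that reaches significance.** Formula: t(0.975, 39) × SD / √40, with t = 2.023.

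- SD 0.10: 2.023 × 0.10 / 6.325 = 0.032 mm
- SD 0.15: 0.048 mm
- SD 0.20: 0.064 mm
- SD 0.30: 0.096 mm

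All are below one step. Holding the SD fixed, they correspond to moving about 32%, 48%, 64% and 96% of readings up one step.

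**Step 2: false-positive rate under shading.** The mean shift is 0.1 × f. Shading only some readings also adds variance of 0.01 × f(1 − f), so the SD becomes √(SD² + 0.01 f(1 − f)), and the noncentrality is 0.1 f × √40 divided by that SD. Worked example for f = 0.25 and SD 0.10:

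- shift = 0.025 mm
- SD = √(0.01 + 0.001875) = 0.109 mm
- noncentrality = 0.025 × 6.325 / 0.109 = 1.45
- rejection probability = about 29%

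Simulation of the same model agrees:

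| SD of change (mm) | f = 0 | f = 25% | f = 50% |
|---|---|---|---|
| 0.10 | 5% | 29% | 79% |
| 0.15 | 5% | 17% | 49–50% |
| 0.20 | 5% | 12% | 32% |
| 0.30 | 5% | 8% | 17% |

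**Step 3: sensitivity.** A simulation that also rounds each reading to 0.1 mm (baseline height assumed mean 0.25, SD 0.08 mm) gives 26%, 16%, 12% and 8% at f = 25%, and 74%, 47%, 31% and 17% at f = 50%. With no shading it gives 4.6% to 5.2%.

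Shifting the mean while leaving the SD unchanged would give 34%, 18% and 12% (f = 25%) and 87%, 54% and 34% (f = 50%) at SD 0.10, 0.15 and 0.20. Those figures are too high because they omit the added variance.

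**Limit of the calculation.** It measures upward shading from any cause. It does not isolate the part due to seeing the baseline number, and the documents give no basis for doing so.

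**The case against.** The strongest reply is that the calculation does not measure this mechanism. An examiner who has just inspected the plug can round a borderline reading up without knowing the Day 0 value. This stands: the table is an illustration of how sensitive the test is, not an estimate of what the fix would remove.

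Direction is not shown either. A visible earlier value could draw the new reading toward it and shrink the change. This also stands. Upward shading is the more likely direction given the expected effect, but no section demonstrates it.

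The documents do not say that investigators look at the earlier page, and Section 11.4 gives no duration for keeping pages in the booklet. White forms could be collected before Visit 3 at some sites. That limits the point to what is possible. It does not supply a safeguard, because collection timing is unstated and source records remain at the site.

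Finally, this is a declared open-label pilot, and its larger limits, a visible plug and no control, would remain. That bears on priority; it is not a reason to leave out a cheap protection for the only primary endpoint.

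A reader might infer that the plan builds in a false-positive rate of a third or more, or that the baseline number will create the primary result. The documents support neither. The rates depend on an assumed SD and assumed shading fractions, and at SD 0.30 mm the excess is small when a quarter of readings are shaded (8% against 5%).

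**Conclusion.** The point holds as a gap in measurement procedure. The plan lets the examiner see the Day 0 tear lake value before reading the follow-up height, and the primary variable is the difference between the two. The influence is possible and probably upward; its size is unknown.

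With n = 40, a two-sided one-sample t-test, no true change and an assumed SD of change of 0.10 to 0.30 mm, one-step upward shading of a quarter of readings from any cause gives a false-positive rate of about 29% down to 8%. Shading of half gives about 79% down to 17%. What share of such shading would come from the visible baseline number cannot be derived from the documents. This is a low-cost improvement, not the correction of an error or contradiction in the plan.

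**What to change.** **Procedure.** Add to Section 7.2.1(e) and to the Visit 2, Visit 3 and Early Exit lists: the examiner measures and states the tear lake height before seeing any earlier tear lake value, whether in the CRF or in the source records, and existing site staff record it. Section 7 limits CRF entries to staff on the delegation form, so the recorder should be listed there. Section 5.4 already asks sites for a dedicated coordinator ("sites should dedicate an individual [Clinical Research Coordinator (CRC)] who is well informed regarding the study design"), but for recruitment and retention, so the recording task would have to be assigned.

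**Forms.** Put the tear lake value on its own CRF page and its own source page for each visit. Amend Sections 11.1 and 11.4 so that earlier tear lake pages are kept from the examiner until that visit's reading is recorded. Monitors keep access for the CRF-to-source comparison in Section 9, and the investigator signs these pages after the subject exits. Slit-lamp and safety pages stay available throughout.

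**Cost.** One separate page per visit in each record and a filing step; no extra assessor, visit or procedure. The benefit is partial: some recall of earlier values, awareness of the plug, any bias in the Day 0 reading itself and the lack of a control all remain, and the study report should say so.
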